Standard initial treatment for glioblastoma currently consists of surgical removal of as much of the MRI contrast-enhancing lesion as can be accomplished safely, followed by radiotherapy and temozolomide (TMZ) chemotherapy for 6 weeks. Unfortunately, early treatment failures occur in 30-50% of patients. This definition of treatment failure is described as an increase in the MRI T1+Gd tumor volume (de Wit, 2004). Immediate post-radiotherapy MRI changes in malignant glioma can mimic tumor progression (Taal, 2008). The incidence of this pseudo-progression in a cohort of malignant glioma patients treated with chemo-radiation with temozolomide is significant (Brandes, 2008). From 28-52% of these patients will demonstrate improvement on subsequent MRI studies when they continue on standard TMZ chemotherapy. This situation defines pseudo-progression as opposed to true disease progression, where continued treatment with temozolomide is associated with continued clinical decline and MRI T1+Gd worsening. Clinicians armed with anatomic MRI imaging alone may wrongly conclude that standard treatment is failing in these patients, leading to cessation of a treatment that is actually working. Also, misdiagnosing pseudo-progression in patients who are responding could risk entering such patients into phase II or III trials of new agents, decreasing the statistical power of the study and potentially leading to falsely positive outcomes. On the other hand, continuing TMZ in the patients that are true progressors wastes their time and physiological resources when they should be offered second line treatment or enrollment in a phase II or III research treatment protocol. Thus, the ability to make the important distinction between progression and pseudo-progression is critical for the care of treated brain tumor patients and could potentially change patient management. In some patients, the neuropathologist who reviews the resected tumor resolves the question of pseudo-progression versus true progression. Ideally, however, noninvasive imaging methods should be developed to answer this question reliably. Our primary hypothesis is that FLT PET/CT should be able to distinguish between when the patient has true tumor progression and needs to change therapy and when the MRI contrast is reflecting pseudo-progression and the patient should continue with TMZ chemotherapy. That way, the 50% or possibly more true progressors could avoid continuing futile TMZ.

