3'-Deoxy-3'-[¹⁸F]fluorothymidine ([¹⁸F]FLT) is a structural analog of the DNA constituent, thymidine (Figure 6.iii.2). It is a radiolabeled imaging agent that has been proposed for investigating cellular proliferation with positron emission tomography (PET). Although [¹⁸F]FLT is not incorporated into DNA, it is trapped in the cell due to phosphorylation by *thymidine kinase 1*, a part of the salvage pathway. As such, it has potential as a marker of proliferating tumor in proportion to the DNA synthesis rate. Therefore, [¹⁸F]FLT is proposed as a radiolabeled imaging probe for *in vivo* assessment of cellular proliferation in malignant tumors using PET. For complete information, please refer to the Investigator's Brochure: "3'-deoxy-3'-fluorothymidine: [¹⁸F]FLT, An Investigational Positron Emission Tomography (PET) Radiopharmaceutical for Injection and intended for use as an *in vivo* diagnostic for imaging active cellular proliferation of malignant tumors."

6.iii.3.c. Rationale

[¹⁸F]FLT is a radiolabeled imaging probe for *in vivo* assessment of cellular proliferation using PET. Preclinical and clinical studies suggest that early imaging of response using this radiopharmaceutical can demonstrate effectiveness of treatment in a variety of tumors. In this protocol, we will assess regional FLT uptake in patients with malignant brain tumors.

[figure not shown]

Figure 6.iii.2. Molecular structures for FLT and thymidine

Specifically, we propose to use [¹⁸F]FLT PET/CT to assess changes in imaging measures in the clinical course of brain tumor patients. Subsequent studies (not part of this trial) could eventually allow treatments to be tailored to the tumor response measured by imaging, eliminating the use, costs and toxicity of ineffective treatments and improving the patient's quality of life. This is our long-term objective. In this protocol, FLT PET/CT imaging measures will be compared with clinical measures of tumor response to test specific hypotheses.

Hypotheses for this protocol.

1. Quantifying tumor proliferation in brain tumors will provide a reliable measure of disease. For example, kinetic analysis of the FLT-PET/CT data will allow distinction between true progression and pseudo-progression in patients with glioblastoma who have finished surgery plus radiotherapy and temozolomide and whose measurable disease by standard MRI after initial treatment has appeared to progress.

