This is not a treatment trial. Patients will be managed according to the plan developed by their treating clinicians. Patients will be treated at the University of Washington clinics where standard of care for treatment calls for surgery, chemotherapy, radiation, or chemoradiation with adjuvant chemotherapy. Standard salvage therapy will be offered patients who progress based on current clinical indications by their clinicians. Salvage therapy includes re-operation, re-irradiation, second line chemotherapy agents or a combination of these options. We will serially image patients using FLT PET/CT for quantifying tumor cellular proliferation at several time points in their clinical course. The times will include baseline and can include mid therapy and up to two scans during the clinical follow-up period after therapy. Standard clinical MR images will be acquired during the therapy schedules as requested by the clinicians. Patients may also undergo research MR imaging.

6.iii.6.a. [¹⁸F]FLT Administration:

[¹⁸F]FLT will be administered in the PET Imaging Suite at the University of Washington Medical Center or at the Seattle Cancer Care Alliance (SCCA). Upon arrival, the patient will have an opportunity to have questions answered regarding the procedure. The patient will have one intravenous line placed prior to [¹⁸F]FLT administration. The patient will then be positioned in the PET scanner followed by a transmission scan using a low-dose CT scan. Then [¹⁸F]FLT will be administered intravenously by a physician. The administered dose will be 0.07 mCi/kg with a maximum of 5 mCi. The drug solution is stored at room temperature in a gray butyl septum sealed, sterile, pyrogen-free glass vial and has an expiration time of 8 hours. The injectable dose of [¹⁸F]FLT will be \leq 0.07 mCi/kg of fluorine-18, not to exceed 5 mCi. In the dose of [¹⁸F]FLT, only a small fraction of the FLT molecules are radioactive. The amount of injected drug is \leq 6.1 μ g (\leq 25 nmol per dose) of FLT. There is no evidence that nonradioactive and radioactive FLT molecules display different biochemical behavior. [¹⁸F]FLT is administered to subjects by intravenous injection of \leq 10 mL. The injection will be infused over approximately 1 minute and followed by a saline flush. The infusion and imaging procedure will be terminated in any patient who exhibits anaphylaxis, significant dyspnea or chest pain.

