The adverse events to be specifically monitored during the infusion include localized discomfort at the IV injection site, pain, respiratory difficulties, flushing, dizziness, pruritus/rash, and any other symptoms that could be secondary to an anaphylactic reaction. The subject will be instructed to report any subjective symptoms or sensory changes noted. All adverse events occurring post [¹⁸F]FLT infusion will be recorded within a 24-hour period.

6.iii.6.b. Study Procedures and Schedule of Events:

6.iii.6.b.1. Initial visits prior to [¹⁸F]FLT PET: Patients who are identified as potential candidates for the [¹⁸F]FLT PET study will be approached to explain the nature of the study and to obtain their written informed consent to be enrolled in the protocol. The following additional patient data will be obtained: tumor location, correlative imaging findings, histologic diagnosis (if available), age at diagnosis, and gender.

6.iii.6.b.2. Day of [¹⁸F]FLT PET Scans: The patient will be positioned supine in the PET/CT scanner for a dynamic scan over the brain. [¹⁸F]FLT PET/CT will be performed using the standard dose of 5 mCi. Patients will have 1 or 2 intravenous lines placed. A low-dose CT scan (PET/CT) will be used for positioning and attenuation correction. The single field of view over the brain will be imaged dynamically for about 90 minutes following the start of a one-minute intravenous infusion of [¹⁸F]FLT. Total patient time, including line placement and imaging is typically 2 hours. During the scan, three venous blood samples will be taken to analyze for FLT metabolites by the method we developed and is detailed in the Investigator's Brochure our previously developed solid phase exchange method that is published on the ACRIN trials website (ref: <http://www.acrin.org/Portals/0/Protocols/6689/imaging/ACRIN%206689%20FLT%20Blood%20Processing%20-20V1.0%20%20%20%20February%202011,%202011.pdf>).

6.iii.6.b.3. After the baseline and follow up [¹⁸F]FLT PET Scans: A follow up phone call will be made by study staff the next day after a [¹⁸F]FLT PET/CT scan to ask about any signs of adverse effects.

6.iii.6.c. General Concomitant Medication and Supportive Care Guidelines

There are no requirements for concomitant medication supportive care as part of this study.

6.iii.6.d. Duration of Therapy:

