The chemical precursor for [¹⁸F]FLT is provided by ABX in single-use, 10 mg vials that are delivered to the custody of [name], the lead radiochemist for this project. They are stored in a controlled temperature refrigerator in a locked and secure room and they are inventoried with a chain of custody maintained from the time of receipt. Each radiosynthesis is done by [name], [name] or their designee and, after passing all required quality control assays, the product [¹⁸F]FLT dose is drawn up under the authority of the nuclear medicine physician co-investigator, [name], [name] or their designee. The quality control tests that must be passed prior to release of the product [¹⁸F]FLT for injection include the pH, radioactive purity, radiochemical purity, specific activity, sterilizing filter integrity, tests for Kryptofix [2.2.2], acetonitrile, acetone, dimethylsulfoxide, endotoxins and particulates. Acceptance criteria are detailed in the CMC section of this IND. The [¹⁸F]FLT dose is drawn up into a syringe, assayed for mCi at time of injection, labeled and passed to the physician investigator who oversees the re-assay of the dose and the administration to the research subject.

6.iii.10. CORRELATIVE / SPECIAL STUDIES

Study data are comprised of imaging parameters from at least two and as many as four [¹⁸F]FLT PET studies.

6.iii.10.a. [¹⁸F]FLT PET/CT Image Analysis

Preliminary data suggests that [¹⁸F]FLT is essentially irreversibly phosphorylated and trapped inside cells during the imaging period. Prior to this point, however, there is a flux of unphosphorylated [¹⁸F]FLT (reversible component). If the rate of phosphorylation (k_3) is low, then the early contribution of perfusion to the measured tumor activity is high. Assuming the phosphorylation rate correlates to the proliferative rate, a high rate of phosphorylation means that the cumulative measured tumor activity should be representative of cellular proliferation.

Volumes of interest (VOIs) will be drawn around the target lesions on the [¹⁸F]FLT images based on the tumor localization on the baseline CT. [¹⁸F]FLT PET studies will be registered based on their corresponding CT transmission scans images, and time activity curves (TACs) will be calculated.

[figure not shown]

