Stable disease	Requires all of the following: does not qualify for complete response, partial response, or progression; stable nonenhancing [T2/FLAIR] lesions on same or lower dose of corticosteroids compared with baseline scan. In the event that the corticosteroid doses was increased for new symptoms and signs without confirmation of disease progression on neuroimaging, and subsequent follow-up imaging shows that the increase in corticosteroids was required because of disease progression, the last scan considered to show stable disease will be the scan obtained when the corticosteroid dose was equivalent to the baseline dose.
Progression	Defined by any of the following: $\geq 25\%$ increase in sum of the products of perpendicular diameters of enhancing lesions compared with the smallest tumor measurement obtained either at baseline (or no decrease) or best response, one stable or increasing doses of corticosteroids*; significant increase in T2/FLAIR nonenhancing lesion on stable or increasing doses of corticosteroids compared with baseline scan or best response after initiation of therapy* not caused by comorbid events (e.g. radiation therapy, demyelination, ischemic injury, infection, seizures, postoperative changes, or other treatment effects); any new lesion; clear clinical deterioration not attributable to other causes apart from the tumor (e.g. seizures, medication adverse effects, complications of therapy, cerebrovascular events, infection, and so on) or changes in corticosteroid dose; failure to return for evaluation as a result of death or deteriorating condition; or clear progression of nonmeasurable disease.

NOTE: All measurable and nonmeasurable lesions must be assessed using the same technique as at baseline.
 
Abbreviations: MRI, magnetic resonance imaging; FLAIR, fluid-attenuated inversion recovery.
 
*Stable doses of corticosteroids include patients not on corticosteroids.
	

Table 6.iii.6 Summary of the Proposed RANO Response Criteria

Criterion	CR	PR	SD	PD
T1 gadolinium enhancing disease	None	$\geq 50\% \downarrow$	$< 50\% \downarrow$ but $< 25\% \uparrow$	$\geq 25\% \uparrow^*$
T2/FLAIR	Stable or \downarrow	Stable or \downarrow	Stable or \downarrow	\uparrow^*
New lesion	None	None	None	Present*
Corticosteroids	None	Stable or \downarrow	Stable or \downarrow	NA ^Δ
Clinical Status	Stable \uparrow	Stable or \uparrow	Stable or \uparrow	\downarrow^*
Requirement for response	All	All	All	Any*

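### For Hypothesis 1, FLT regions localized from the baseline CT can miss the new or enlarged MRI enhancement that the scan is meant to classify

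*Combined protocol and SAP*

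**What the plan says.** **VOI rule.** Section 6.iii.10.a has target lesions outlined on the FLT images, "based on the tumor localization on the baseline CT". Serial FLT studies are then aligned with each other: "PET studies will be registered based on their corresponding CT transmission scans images". No section registers MRI to PET, uses MRI to place a region, or says how a lesion that is new or larger at follow-up gets one.

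**The CT.** The only CT described for the study scans is in sections 6.iii.6.a and 6.iii.6.b.2: "A low-dose CT scan (PET/CT) will be used for positioning and attenuation correction".

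**The question.** Section 6.iii.3.a states: "Our primary hypothesis is that FLT PET/CT should be able to distinguish between when the patient has true tumor progression". Hypothesis 1 in 6.iii.3.c concerns glioblastoma patients "whose measurable disease by standard MRI after initial treatment has appeared to progress". Section 6.iii.14.b compares mean FLT flux between true progression and pseudo-progression. Section 6.iii.14.c enters the FLT parameters measured shortly after therapy into a logistic model for progression.

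**How progression is seen.** Of early treatment failure, 6.iii.3.a says: "This definition of treatment failure is described as an increase in the MRI T1+Gd tumor volume". Table 6.iii.5 also counts "any new lesion" as progression.

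**MRI availability.** Section 6.iii.6 says: "Standard clinical MR images will be acquired during the therapy schedules as requested by the clinicians".

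**The concern.** The tissue that Hypothesis 1 must classify is enhancement seen on MRI after treatment. The tissue sampled is localized before treatment, on a different modality. The two can differ, and the plan has no step that brings them together.

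A true progressor whose tumor has grown outside the baseline region could be read as treated tissue. That would shrink the flux difference between the groups and could make a useful marker look uninformative. The study is meant to inform larger trials, so a false negative here would carry forward. The power text in 6.iii.14.b assumes one VOI per subject, so no second region is planned as a safeguard.

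**Working it through.** The plan gives no figure for VOI placement, so there is none to reproduce. The check compares the passages and then asks how far the effect could range.

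**1. Two readings of the rule.** The text does not say whether the outline is fixed at baseline or redrawn at each scan.

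| Reading | Consequence for Hypothesis 1 |
|---|---|
| Baseline localization is carried forward | New or expanded enhancement outside it is not sampled |
| Outline is redrawn to follow FLT uptake | FLT-avid growth is included, but the variable under test sets the boundary, and a low-uptake pseudo-progressing lesion offers little edge to draw |

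These are alternatives and do not add together. Neither ensures that the MRI lesion is what gets measured.

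**2. Share of the enhancing lesion outside a carried-forward region.** Table 6.iii.5 sets progression at a 25% rise in the product of diameters, measured from the smallest measurement (baseline or best response).

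- New lesion outside the baseline region: 100% outside.
- Isotropic growth with no earlier shrinkage or resection: the volume ratio is 1.25^1.5 = 1.398, and the share outside is 1 − 1/1.398 = 0.284, or 28%.
- Shrinkage to 50% of the baseline product, then a 25% rise: 0.50 × 1.25 = 0.625 of baseline. If concentric, 0% is outside.

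The range is therefore 0% to 100%, and the documents do not say how often each case occurs.

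**3. What the region would read in the middle case.** The inputs are the 6.iii.14.b means: 0.017 for recurrence and 0.004 for radionecrosis. Assume also that all viable tumor lies outside the old margin.

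- Baseline region: 0.004, a contrast with radionecrosis of 0.
- Whole MRI lesion: 0.716 × 0.004 + 0.284 × 0.017 = 0.0077, a contrast of 0.0037.
- New enhancement alone: 0.017, a contrast of 0.017 − 0.004 = 0.013.

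These values hold only under the no-shrinkage, no-resection and isotropic-growth conditions of that case. If regrowth is inside the old margin, the baseline region already contains it.

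**4. Effect on power, as a range.** Let f be the fraction of the between-group contrast that the region captures, with the SD unchanged. The documents give no f. The calculation is a two-sample t-test, two-sided 5%, 12 versus 18 patients. That is the plan's 40:60 split of 30, treating all 30 as progressing glioblastoma cases.

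| f | Plan's effect, 0.99 × f | Full recurrence–radionecrosis contrast, (0.017 − 0.004)/0.005 = 2.6, × f |
|---|---|---|
| 1.0 | 73% | >99.9% |
| 0.75 | 49% | 99.9% |
| 0.5 | 25% | 92% |
| 0.25 | 10% | 39% |

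The first row does not reproduce the plan's stated power of about 95%. That is a separate matter and does not bear on VOI placement. What the table shows is that the loss depends heavily on both f and the true contrast.

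**The case against.** A reader might infer that expanded enhancement is necessarily missed, and by about 28% of its volume. The documents do not support that.

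- **The outline is not clearly frozen.** The rule places regions on the FLT images and uses the baseline CT to localize them. It does not say that the contour is copied forward.
- **The 28% uses a special case.** Progression is measured from the smallest measurement, and standard glioblastoma treatment starts with resection, so regrowth may lie wholly inside the baseline region. The 25% threshold also comes from the RANO table, whereas 6.iii.14.b selects Hypothesis 1 patients by Macdonald criteria, whose thresholds the documents do not state.
- **Low-dose is an inference.** The sentence on VOIs says only baseline CT. The low-dose description comes from the scan procedures.
- **Recurrent tumors are eligible.** If the first scan is made at recurrence, the baseline CT is contemporaneous with the finding.
- **MRI enhancement is not the whole of progression.** Table 6.iii.5 also allows T2/FLAIR change, nonmeasurable disease or clinical decline. In the illustration above, a whole-lesion MRI region recovers only 0.0037 of the 0.013 contrast.
- **The images can be re-read.** If the dynamic data are kept, regions can be redrawn later.

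All of this stands as a limit on the size of the claim. It does not supply the missing rule. A fixed region suits percentage change within a lesion, but Hypothesis 1 compares flux between groups at apparent progression and does not need one. Redrawing regions after the results are known is a weaker safeguard than a rule set beforehand.

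**Conclusion.** The point holds in this form: the only stated VOI rule does not ensure that FLT flux for Hypothesis 1 is measured in the MRI lesion whose nature is in question. New or expanded enhancement can be missed if the baseline localization is carried forward. If the outline follows uptake, the test variable influences its own sampling region.

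The size of the bias cannot be computed from the documents. It runs from little or nothing, when regrowth is inside the baseline margin or the baseline scan is made at recurrence, to complete loss for a new lesion outside the region. The 28% and 0.0077 figures and the power table are illustrations under the assumptions stated with them, not estimates for this trial. The change is worth making because it is cheap and protects the question that the protocol calls its primary hypothesis.

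**What to change.** Amend 6.iii.10.a for Hypothesis 1 and for the post-therapy FLT parameters in the progression model of 6.iii.14.c:

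- Define the VOI on the clinical MRI that showed apparent progression, or the one nearest the FLT scan, co-registered to PET through the CT.
- Include new and enlarged enhancing lesions.
- Draw the outline without reference to FLT uptake, then read K1, KFLT and SUV inside it.
- Record the interval between MRI and FLT scan.

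Keep the baseline-localized VOI for the percentage-change analyses, and state whether its contour is carried forward or redrawn.

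The cost is wording plus contouring and one MRI-to-PET registration per relevant scan. No new imaging is needed, since the MRIs are acquired clinically. There are three small downsides. The VOI will differ across time points, which the retained baseline VOI covers. The MRI-to-PET interval will vary, because MRI timing is left to the clinicians. Progression called only on T2/FLAIR or clinical grounds will have no enhancing region, so the plan should say how those patients are handled.

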Stable disease	Requires all of the following: does not qualify for complete response, partial response, or progression; stable nonenhancing [T2/FLAIR] lesions on same or lower dose of corticosteroids compared with baseline scan. In the event that the corticosteroid doses was increased for new symptoms and signs without confirmation of disease progression on neuroimaging, and subsequent follow-up imaging shows that the increase in corticosteroids was required because of disease progression, the last scan considered to show stable disease will be the scan obtained when the corticosteroid dose was equivalent to the baseline dose.
Progression	Defined by any of the following: $\geq 25\%$ increase in sum of the products of perpendicular diameters of enhancing lesions compared with the smallest tumor measurement obtained either at baseline (or no decrease) or best response, one stable or increasing doses of corticosteroids*; significant increase in T2/FLAIR nonenhancing lesion on stable or increasing doses of corticosteroids compared with baseline scan or best response after initiation of therapy* not caused by comorbid events (e.g. radiation therapy, demyelination, ischemic injury, infection, seizures, postoperative changes, or other treatment effects); any new lesion; clear clinical deterioration not attributable to other causes apart from the tumor (e.g. seizures, medication adverse effects, complications of therapy, cerebrovascular events, infection, and so on) or changes in corticosteroid dose; failure to return for evaluation as a result of death or deteriorating condition; or clear progression of nonmeasurable disease.

NOTE: All measurable and nonmeasurable lesions must be assessed using the same technique as at baseline.
 
Abbreviations: MRI, magnetic resonance imaging; FLAIR, fluid-attenuated inversion recovery.
 
*Stable doses of corticosteroids include patients not on corticosteroids.
	

Table 6.iii.6 Summary of the Proposed RANO Response Criteria

Criterion	CR	PR	SD	PD
T1 gadolinium enhancing disease	None	$\geq 50\% \downarrow$	$< 50\% \downarrow$ but $< 25\% \uparrow$	$\geq 25\% \uparrow^*$
T2/FLAIR	Stable or \downarrow	Stable or \downarrow	Stable or \downarrow	\uparrow^*
New lesion	None	None	None	Present*
Corticosteroids	None	Stable or \downarrow	Stable or \downarrow	NA ^Δ
Clinical Status	Stable \uparrow	Stable or \uparrow	Stable or \uparrow	\downarrow^*
Requirement for response	All	All	All	Any*

Abbreviations: RANO, Response Assessment in Neuro-Oncology; CR, complete response; PR, partial response; SD, stable disease; PD, progressive disease; FLAIR, fluid-attenuated inversion recovery; NA, not applicable
* Progression occurs when this criterion is present.
Δ Increase in corticosteroids alone will not be taken into account in determining progression in the absence of persistent clinical deterioration.

The primary analysis variables for the study are:

- Percentage change in K_1 , FLT flux and SUV for [¹⁸F]FLT PET/CT
- Assessment of clinical response per the response criteria listed above.
- Survival

Secondary analysis variables are:

- Heterogeneity in K_1 , FLT flux and SUV for [¹⁸F]FLT PET/CT at baseline.
- Comparison of heterogeneity at different times

6.iii.13. DATA REPORTING / REGULATORY CONSIDERATIONS

Adverse event lists, guidelines, and instructions for AE reporting are described in Section 6.iii.8. The Principal Physician Investigator is responsible for maintaining complete and timely, HIPAA-compliant electronic records of clinical and image datasets.

6.iii.14. STATISTICAL CONSIDERATIONS

6.iii.14.a. Study Description

This is a study involving [¹⁸F]FLT PET/CT imaging of patients with brain tumors at different times during the course of standard treatment. Thirty patients with brain tumors and who are planning standard therapy with surgical resection, chemotherapy or radiotherapy or any combination, will be enrolled. We will evaluate the values for percentage changes in [¹⁸F]FLT PET measures observed following 1-3 weeks of therapy, shortly after finishing therapy and at time of

recurrence or at one year, whichever comes first and explore associations between [¹⁸F]FLT PET parameters and their changes and clinical outcome.

6.iii.14.b. Power Calculations

For hypotheses 2 and 3, we will use patient survival as our outcome variable and the analysis will be based on the Cox proportional hazards model with adjustment for confounding. We have estimated that with 30 patients our study will have power characteristics presented in Table 6.iii.7. These calculations used a value for the study effect of 0.75.

Table 6.iii.7. Power calculation for measuring response	FU=2 yrs	FU=7 yrs
Power without cofounders	0.79	0.80
Power using cofounders, including FDG PET/CT	0.87	0.83
Effect of 15% measurement error	0.89	0.84

The analysis of data for these hypotheses involves within-subject changes where the variance in values will be less than between-subject FLT results that we have published. Furthermore, this power analysis has assumed that only data from a single volume of interest (VOI) for each subject will be used. In the context of our aims, this could be considered inefficient. In many subjects it will be possible to include data from spatially well-separated and hence substantially uncorrelated sub-regions within large tumors (Spence, 1998) as distinct sampling units for consideration with this hypothesis. Notwithstanding the additional variability that sub-region measurements will have, it is likely that some gains in statistical precision can be realized by this approach. Thus the 90% power estimate is conservative.

Hypothesis 1. Among GBM patients identified as progressing according to Macdonald criteria at 1-month follow-up, the mean FLT flux in true progression cases will be compared to the corresponding mean in the pseudo-progression cases. Preliminary data indicate that 40% of MRI diagnosed progression can be expected to be pseudo-progression. Our data on recurrence vs radionecrosis for KFLT recurrences showed a mean of 0.017 and a standard deviation of 0.005 (Spence, 2006). The mean of the radionecrosis group was 0.004, roughly one-quarter for that for recurrences. Thus, conservatively, assuming that pseudo-progressors showed even a 30% increase over the mean KFLT value, the expected difference between the groups would be 0.017×0.3 or about 0.005. From this, the expected standardized effect is 0.99. Using a 2-sample t-test with significance level of 5% for assessment of the hypothesis, the power of our study is about 95%.

6.iii.14.c. Analysis Plan

Percentage change between pre-treatment and post-therapy measurements will be computed for [¹⁸F]FLT PET/CT measures of transport, K₁, and flux (KFLT). Log transformations will be considered if the rates of change are highly skewed. Outcome analysis studies are directed toward predicting tumor response. In the case of progression, a multivariate logistic regression will be used to produce an analysis of how the combination of standard diagnostics plus the FLT parameters (K₁, KFLT, SUVmean) obtained shortly after therapy can best be combined to

obtain a prognostic variable for determination of progression. Although the prognostic variable will provide a direct assessment of the probability of response for an individual patient, we will also develop a ROC characterization of its diagnostic performance. We fully appreciate that the small number of patients means that this analysis may suffer from a lack of power but it should be useful in planning a larger follow-up if the results are encouraging.

A similar approach will be used for survival analysis.. Here we will use multivariate Cox regression analysis with both baseline and follow-up variables to be considered.

The heterogeneity of the within-tumor proliferation obtained by application of the elliptical heterogeneity measure developed by Eary et al (2008) will be used in a secondary analysis.

6.iii.14.d. Stratification Factors

Not Applicable.

6.iii.14.e. Reporting and Exclusions

Evaluation of Toxicity: All patients will be evaluable for toxicity from their [¹⁸F]FLT PET.

6.iii.15. LITERATURE CITED

Carlson RW. Sequencing of endocrine therapies in breast cancer--integration of recent data. *Breast Cancer Res Treat* 2002; 75 Suppl 1 S27-32; discussion S33-5.

Carlson RW, Allred DC, Anderson BO, Burstein HJ, Carter WB, Edge SB, Erban JK, Farrar WB, Goldstein LJ, Gradishar WJ, Hayes DF, Hudis CA, Jahanzeb M, Kiel K,

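### Table 6.iii.7 shows power rising under 15% measurement error (0.87/0.83 to 0.89/0.84); classical error in the tested FLT predictor must lower it, so the row, read as power, and the 90% claim are unsupported

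*Combined protocol and SAP*

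**What the plan says.** Section 6.iii.14.b covers hypotheses 2 and 3, with survival as the outcome: "the analysis will be based on the Cox proportional hazards model with adjustment for confounding". It introduces the table with "We have estimated that with 30 patients our study will have power characteristics presented in Table 6.iii.7" and adds "These calculations used a value for the study effect of 0.75". The caption is "Table 6.iii.7. Power calculation for measuring response". The entries are:

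| Row | 2 years | 7 years |
|---|---|---|
| "Power without cofounders" | 0.79 | 0.80 |
| "Power using cofounders, including FDG PET/CT" | 0.87 | 0.83 |
| "Effect of 15% measurement error" | 0.89 | 0.84 |

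No text explains the third row, says which variable carries the error, or defines 15%. The paragraph after the table argues that further precision may be gained from within-subject changes and tumour sub-regions, and ends: "Thus the 90% power estimate is conservative".

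**The concern.** The row that adds measurement error has the highest value in both columns. FLT measures are the predictors under test, and noise in a tested predictor dilutes its association with survival. The row should therefore lie below the confounder-adjusted row.

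This matters for two reasons. Measured FLT values contain error, so of the three rows this one comes closest to describing the study that will be run. And 0.89 is the table entry nearest to the 90% quoted afterwards; no other entry exceeds 0.87. The schema (6.iii.1) says that promising data will be used to design larger trials, so an inflated planning figure could be carried forward.

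**Working it through.** **Inputs.** The table entries, 30 patients and the effect of 0.75 come from 6.iii.14.b. No alpha is given for the Cox calculation; I assume two-sided 5%, the level stated for the hypothesis 1 t-test. For one reading of 15% I borrow the KFLT mean of 0.017 and SD of 0.005 from hypothesis 1, a coefficient of variation (CV) of 0.005/0.017 = 29%.

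**Can the table's level be reproduced?** Not from what is given. With D deaths, power = Φ(√D × SD × |β| − 1.96). Taking all 30 patients as deaths:

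- Continuous predictor, 0.75 as log hazard ratio per SD: √30 × 0.75 = 4.108, power 0.984.
- Continuous predictor, 0.75 as hazard ratio per SD: √30 × 0.288 = 1.576, power 0.35.
- Equal two-group split (SD 0.5), 0.75 as log hazard ratio: power 0.537.
- Equal two-group split, 0.75 as hazard ratio: power 0.121.

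None of these is 0.79/0.80. The number of deaths, the effect scale, the confounder correlation and alpha would all be needed. The direction check below needs none of these except alpha.

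**Direction.** The non-centrality implied by a stated power is 1.96 + z(power):

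- 0.87 → 3.086; 0.89 → 3.186
- 0.83 → 2.914; 0.84 → 2.954

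Classical, non-differential error in the tested predictor multiplies non-centrality by √reliability. Moving from the second row to the third therefore implies:

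- 2 years: (3.186/3.086)² = 1.066
- 7 years: (2.954/2.914)² = 1.028

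Both exceed 1, which is impossible.

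**Size.** From 0.87/0.83, power with error = Φ(non-centrality × √reliability − 1.96):

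| Meaning given to 15% | Reliability | 2 years | 7 years |
|---|---|---|---|
| Error SD is 15% of true SD | 1/(1 + 0.15²) = 0.978 | 0.863 | 0.822 |
| Error variance is 15% of true variance | 1/1.15 = 0.870 | 0.821 | 0.776 |
| Error variance is 15% of total variance | 0.850 | 0.812 | 0.766 |
| Error CV 15%, true CV 29% | 0.294²/(0.294² + 0.15²) = 0.794 | 0.785 | 0.738 |
| Error CV 15%, observed CV 29% | 1 − 0.15²/0.294² = 0.740 | 0.756 | 0.708 |

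The stated values exceed these by 0.89 − 0.863 = 0.027 and 0.84 − 0.822 = 0.018 at the mild end, and by 0.89 − 0.756 = 0.134 and 0.84 − 0.708 = 0.132 at the severe end. One-sided testing changes the results by no more than about 0.02.

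**Simulation check.** Cox models with 30 patients, log hazard ratio 0.75 per SD, one confounder, about 20% censoring and 3,000 runs per setting covered three confounder correlations and three reliabilities. Error in the FLT predictor lowered power in all nine settings. With an uncorrelated confounder, power went from 0.846 to 0.838, 0.849 to 0.783 and 0.846 to 0.739 at reliabilities 0.978, 0.87 and 0.794.

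**Multiplier reading.** If the third row scales the second, power is 0.87 × 0.89 = 0.77 and 0.83 × 0.84 = 0.70.

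**The case against.** **The row may not be a power.** The first two labels begin with the word power and the third does not. As a multiplier, the row gives 0.77/0.70, close to the loss expected from a 15% CV. This cannot be excluded. The caption, the lead-in sentence and the 90% statement favour power, however, and under the multiplier reading the 90% statement has no support.

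**A reader might infer that power can only fall, whichever row is the comparator and wherever the error sits.** That goes too far. The second row already rises above the first when confounders enter, so if the third row means confounders plus error, exceeding the first row is no anomaly. Only the second row is like for like, and the rise over it is just 0.02 and 0.01. Error confined to a correlated confounder can also raise the rejection rate (0.798 to 0.822 in one simulated setting). That comes from residual confounding, and the plan does not say it was intended.

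**The rise could be simulation noise.** At 1,000 runs the standard error of such a difference is about 0.015. The plan mentions no simulation, and noise would not make the row valid.

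**A reader might take a specific corrected figure, such as 0.79/0.74, from the table above.** The documents do not support one. The 29% CV describes between-patient KFLT levels in recurrences, whereas hypothesis 2 concerns within-subject change. The starting values 0.87/0.83 cannot be reproduced. If 0.75 was standardised on an observed SD, error is already included and a second adjustment would count it twice; even then, adding the error already counted would not raise power.

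**A reader might also solve the formula backwards for the number of deaths.** With 30 deaths the formula gives 0.984 but a simulation gives 0.92, so it is too rough at this sample size.

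**This is a pilot.** Section 6.iii.4.d accepts that limited accrual affects power, and nothing shows that this row set the sample size. That limits the consequence, but the plan still states a power and calls it conservative.

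**Conclusion.** The point holds. Read as power, with classical error in the tested FLT predictor, the third row is wrong in direction: it requires reliabilities of 1.07 and 1.03. Confidence in the direction is high. Confidence in the size is low, because 15% is undefined; across the readings tried, with a two-sided 5% test and 0.87/0.83 taken as the error-free powers, the overstatement is about 2 to 13 points. If the row is a multiplier, the powers are about 0.77/0.70 and the fault is one of labelling. On either reading the table no longer supports the 90% figure. The arguments from sub-regions and within-subject variance might recover some precision, but the plan does not quantify them.

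**What to change.** In 6.iii.14.b, state which variable carries the error, what 15% means, and whether the third row is a power or a multiplier. Give alpha, the number of deaths assumed at each follow-up time, and the scale of the 0.75 effect. Recompute the third row so that it lies below the matching error-free row, name that row, and label the result as power. Replace the sentence calling 90% conservative with the recomputed error-adjusted power. The sponsor must supply the values, since the documents do not determine them.

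The cost is one table and one sentence, and a less favourable stated power. Patients and procedures are unaffected.
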